# 5.2. Statistical software

Analyses will be conducted primarily using the Statistical Packages of the Social Sciences (IBM SPSS v28.0).

# 5.3. Statistical analyses of primary and secondary endpoints

# Patient/ participant characteristics

Description of the baseline characteristics will be presented by treatment group. Discrete/ factor variables will be summarised by frequencies and percentages. Percentages will be calculated according to the number of participants for whom data are available. Continuous variables will be summarised by using mean and SD, and median and interquartile range (Q1-Q3).

Data that will be gathered include the following:

- Age
- Sex
- Pure tones average (based on audiogram performed by the audiologist)
- Ethnicity
- Level of previous hearing aid experience (Yes/No and duration)
- English proficiency (EF SET English proficiency score)
- Self-perceived degree of hearing loss (mild or moderate)

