### 3.3. Sample size

This study aims to recruit 60 people (approximately 30 people in each group) with parallel allocation to the self-fit and audiologist fit groups. Sample size estimation is based on a previous OTC trial conducted by Sabin et al. 2020, who recruited similar sample sizes .

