# 3.4. Randomization and blinding

Participants will be randomized into the self-fit or audiologist fit group using a random number generator. Due to the nature of the study and requirement for audiologist control over the settings in the audiologist-fit group, blinding will not be possible.

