# 4.1.2. International Inventory for Hearing Aids (IOI-HA)

Self-report questionnaires such as the IOI-HA determine wearer-oriented measures and assess how well a person believes their hearing problems have been addressed by means of the benefit derived from their hearing aids (3). Participants will complete this questionnaire at the end of the first and second field trials. Their responses are based on their experience with the study device.

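### Prior hearing aid experience and pure-tone average are collected but enter no outcome comparison; pre-specified adjustment would be a cheap, modest gain, most relevant to IOI-HA, which has no baseline score.

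*Combined protocol and SAP*

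**What the plan says.** - **Collected.** Section 5.3, under participant characteristics, lists "Level of previous hearing aid experience (Yes/No and duration") and "Pure tones average (based on audiogram performed by the audiologist") among the baseline data. The only use given there is descriptive: "Description of the baseline characteristics will be presented by treatment group".
- **Analysis.** The rest of section 5.3 compares the arms by independent-samples t-test or Mann-Whitney U test, chosen by a normality check, for APHAB, QuickSIN and DIN. IOI-HA is compared by Mann-Whitney U because its responses are ordinal. No model, covariate, subgroup or confidence interval is described.
- **Allocation.** Section 3.4: "Participants will be randomized into the self-fit or audiologist fit group using a random number generator". No strata, blocks or minimisation are mentioned.
- **Size.** Section 3.3: "This study aims to recruit 60 people (approximately 30 people in each group) with parallel allocation".
- **Baseline scores.** Table 1 gives APHAB, QuickSIN and DIN a baseline measurement. IOI-HA has none; section 4.1.2 says "Participants will complete this questionnaire at the end of the first and second field trials".
- **Who can enter.** Section 3.5 sets no limit on previous hearing aid use, so new and experienced users can both be enrolled. PTA may lie anywhere between the normal-hearing and severe-loss exclusions.

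**The concern.** With about 30 people per arm and no described stratification, the arms can differ by chance in the share of experienced users or in degree of hearing loss. If either variable is related to outcome, part of an observed difference between arms then reflects who was allocated where. An unadjusted comparison can neither correct for this nor remove the outcome variance that these variables explain.

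For APHAB, QuickSIN and DIN, the planned benefit scores take some account of the starting level. IOI-HA is compared on raw follow-up scores, so nothing in its planned analysis absorbs a baseline difference.

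Timing matters too. The trial is unblinded. If an imbalance appears in the baseline table and adjustment is added afterwards, it will look data-driven.

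**Working it through.** **The plan's own figure.** The 60 participants cannot be reproduced. Section 3.3 says only "Sample size estimation is based on a previous OTC trial" and gives no power, SD, expected effect or dropout. Working backwards, 80% non-inferiority power at 30 per arm (one-sided 2.5%, true difference 0) needs SD ≤ margin / [(1.96 + 0.842) × √(2/30)] = margin / 0.7234. That is 22.5 for APHAB (margin 16.3), 1.38 for IOI-HA (margin 1) and 2.49 dB for QuickSIN and DIN (margin 1.8). With no SD stated, the plan documents no reserve of precision.

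**Chance imbalance in prior experience.** Inputs: 30 per arm (section 3.3) and an assumed share of experienced users. A gap of 20 percentage points is 6 people of 30. With X1 and X2 independent Binomial(30, p), P(|X1 − X2| ≥ 6) is:

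| p (assumed) | Probability |
|---|---|
| 0.3 | 0.120 |
| 0.4 | 0.147 |
| 0.5 | 0.155 |

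Fixing the total number of experienced users at 18, 24 or 30 gives 16%, 19% and 20% instead. Those totals are even, so a gap of exactly 6 is possible; neighbouring odd totals give about 8% to 12%. The binomial figures average over both.

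**Chance imbalance in PTA.** The standardised difference has standard error √(2/30) = 0.258. So P(|difference| > 0.25 SD) = 33% and P(|difference| > 0.5 SD) = 5.3%.

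**What an imbalance does.** Suppose prior experience shifts an IOI-HA item by 0.25, 0.5 or 1 point (assumed). A 20-point gap then moves the estimate by 0.2 × that shift = 0.05, 0.1 or 0.2 points, against a margin of 1. For the planned two-sided 5% test, take a covariate correlated r with outcome and imbalanced by 0.5 SD. The test statistic shifts by 0.5r/0.258 and has conditional SD √(1 − r²). The conditional false-positive rate is about 8% at r = 0.3 and 13% at r = 0.5 (r assumed). At 0.25 SD it stays near 5%.

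**Gain from adjustment.** Ignoring estimation cost, CI width scales by √(1 − R²): 0.949, 0.894 and 0.837 at R² of 10%, 20% and 30%, or 5%, 11% and 16% narrower. Estimating k covariates from 60 people adds chance correlation with arm and lost degrees of freedom. Simulation with normal covariates at 30 per arm puts that cost at a factor of about 1.018 for k = 2 and 1.028 for k = 3. Net change in mean CI width:

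| R² (assumed) | Two covariates | Three covariates |
|---|---|---|
| 0% | 2% wider | 3% wider |
| 10% | 3% narrower | 2% narrower |
| 20% | 9% narrower | 8% narrower |
| 30% | 15% narrower | 14% narrower |

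Break-even R² is 1 − 1/1.018² = 3.5% for two covariates and 1 − 1/1.028² = 5.4% for three, so roughly 4% to 5%. For APHAB, QuickSIN and DIN, the R² that counts for these two variables is what they explain beyond the unaided baseline score.

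**The case against.** An unadjusted comparison in a randomised trial is legitimate. Averaged over randomisations it is unbiased and keeps its type I error, and the plan contradicts itself nowhere on this point. That stands, and it limits the point to an efficiency improvement. A reader might infer that the planned tests are biased or invalid; the documents do not support that.

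Four other limits also stand.

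- A reader might take prior experience and PTA to be the main prognostic information for IOI-HA. No section says that either predicts any outcome. Unaided APHAB, QuickSIN and DIN, age, English proficiency and self-perceived degree of loss are also available at baseline.
- Calling the variables wholly unused goes too far. Both are tabulated by arm, so imbalance would be visible, and PTA also serves as an eligibility criterion. The lack of stratification is inferred from section 3.4 naming only a random number generator.
- The plan specifies no confidence interval to set against its margins. The precision argument therefore takes full effect only once the margins in section 4.3 are tested with an interval, which is a separate matter.
- Section 5.3 gives a reason for the rank test on IOI-HA. A linear model there has to be justified or paired with an ordinal one.

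**Conclusion.** The point holds as a low-severity improvement. Two pre-randomisation variables are already being collected, no outcome comparison uses them, and IOI-HA has no baseline score to adjust for instead. The cost is lost precision and exposure to chance imbalance. Under the ranges shown, a sizeable gap in prior experience is uncommon but not rare, and its likely effect on an IOI-HA estimate is small against the 1-point margin. The net gain in precision runs from slightly negative to moderate.

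The share of experienced users, the R² values, the covariate-outcome correlations and the effect of experience on IOI-HA are all assumptions, because the documents give none of them. The calculations also assume a 30/30 split. If allocation is simple and unblocked, a 25/35 or more uneven split has a probability of about 25%.

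**What to change.** Pre-specify the following, dated before outcomes are compared by arm:

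- **APHAB, QuickSIN and DIN, at each visit:** a linear model with arm, the unaided baseline score, prior hearing aid experience (yes/no) and PTA. Compare the adjusted mean difference and its 95% CI with the stated margin.
- **IOI-HA, at each visit:** a linear model with arm, prior experience and PTA, with unaided APHAB as a possible further covariate. The linear model yields a mean difference that can be set against the 1-point margin, which a Mann-Whitney U test does not. Add a proportional-odds model as a check, since the items are ordinal.
- **Sensitivity analysis:** report the unadjusted difference alongside each adjusted one.

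Stratifying allocation by prior experience is an alternative only if enrolment has not begun.

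The cost is a few sentences of SAP text and two or three of the 58 residual degrees of freedom, with no new data, visits or participants. If the covariates turn out to explain almost nothing, the interval is about 2% to 3% wider.

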# Self-reported hearing aid difficulties

Primary endpoint analyses include the self-reported benefit using the APHAB. Benefit is determined by calculating the APHAB scores conducted at the aided assessment (2-week and 6-week follow-ups) from the baseline scores. The primary endpoint data for all the scores measured at all time points (raw scores), along with the calculated benefit scores (unaided-aided) will be continuous variables. Data will be assessed for normality using the Shapiro Wilk's test. For non-normally distributed variables, non-parametric comparisons between groups will be completed using the Mann Whitney *U* test. For normally distributed variables, comparisons will be done using the independent samples *t*-test.

Effect sizes will be calculated for normally distributed variables, where differences were significant. Cohen's *d* is the primary metric for determining effect sizes of normally distributed variables, for which the values of 0.8, 0.5 and 0.2 are interpreted as large, medium and small effect sizes, respectively. The following formula will be used:

$$d = \frac{M1 - M2}{SDpooled}$$

Effect sizes for non-normally distributed variables will be calculated using effect size *r* for non-parametric tests, calculated using the following formula:

$$z/\sqrt{N}$$

IOI-HA (secondary endpoint) will be conducted at 2- and 6-weeks post hearing aid fitting. IOI-HA data are ordinal response categories and will, therefore, be analysed using non-parametric Mann Whitney U tests for comparison between the two groups.

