# 4.1.1. Abbreviated Profile of Hearing Aid Benefit (APHAB)

This questionnaire quantifies a wearer's self-reported difficulty with communication in everyday communication scenarios (2). Therefore, a representative and valid means of measuring the effectiveness of the study device.

Participants will complete this questionnaire unaided at the end of the first visit and then again at the end of the first and second field trials. Their responses are based on their experience with the study device.

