### 4.2.1. QuickSIN

Several aspects of the QuickSIN test make it suitable for use in assessing comparable improvement of speech-in-noise performance. (1) It is designed to be presented above average conversational level (2) It uses a wide range of SNRs, and (3) the multi-talker background noise represents a common and challenging communication situation. QuickSIN is reported in terms of SNR loss, the increase in SNR required to understand speech in noise compared to persons with normal hearing; higher SNR loss indicates a poorer outcome (4).

SNR loss will be measured unaided at the initial assessment for all participants (prior to the random allocation process). Twice thereafter the aided SNR Loss will be measured. The first aided measurement as per initial fitting settings at the 3rd visit following the post 2-week field trial for the AF and SF groups. The second SNR loss will be measured with

the hearing aids set to the user's preferred setting at the 4th visit, post the 6-week field trial for both groups.

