# 4.2.2. Digits-in-Noise

Since the QuickSIN was developed in American English, one concern was that South African participants could have difficulty recognizing the words due to differences in dialect. Therefore, in addition to the QuickSIN, speech-in-noise performance will be measured using the South African English Digits-in-Noise test (DIN) (5,6). The DIN unaided and aided results will be measured following the same procedure as set for performing the QuickSIN).

Table 1. Timing of the assessments						
Visit	Baseline	Hearing Aid Fitting	2-week follow- up	6-week follow- up		
Pure tone audiometry	Х					
APHAB	X		Х	X		
IOI-HA			X	X		
QuickSIN	X		Х	Х		
DIN	X		X	X		
Real-Ear Measurement		Х		Х		

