# Behavioral outcome measures

Speech recognition scores will be conducted at baseline and at the 2- and 6-week follow ups. Raw scores will be gathered (continuous variables). Additionally benefit scores will be determined by subtracting aided from aided scores. All variables are continuous and will be assessed for normality. For non-normally distributed variables, non-parametric comparisons between groups will be completed using the Mann Whitney *U* test. For normally distributed variables, comparisons will be done using the independent samples *t*-test.

Effect sizes will be calculated for normally distributed variables, where differences were significant. Cohen's *d* is the primary metric for determining effect sizes of normally distributed variables, for which the values of 0.8, 0.5 and 0.2 are interpreted as large, medium and small effect sizes, respectively. The following formula will be used:

$$d = \frac{M1 - M2}{SDpooled}$$

Effect sizes for non-normally distributed variables will be calculated using effect size r for non-parametric tests, calculated using the following formula:

$$z/\sqrt{N}$$

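### APHAB, QuickSIN and DIN use the baseline only by subtraction, and a normality test picks means or ranks; one pre-fixed ANCOVA would answer in margin units at every visit, usually more precisely

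*Combined protocol and SAP*

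**What the plan says.** Section 4.3 frames the alternatives for APHAB, QuickSIN and DIN as non-inferiority of self-fit (SF) to audiologist-fit (AF) at 2 and 6 weeks. The margins are 16.3 points for APHAB and 1.8 dB for the two speech-in-noise tests.

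Section 5.3, under Self-reported hearing aid difficulties, opens with "Primary endpoint analyses include the self-reported benefit using the APHAB". It lists raw scores at all time points, "along with the calculated benefit scores (unaided-aided) will be continuous variables". A Shapiro-Wilk test then selects the method: "For non-normally distributed variables, non-parametric comparisons between groups will be completed using the Mann Whitney" U test, and otherwise an independent-samples t-test. The effect sizes are Cohen's d, after a significant difference, or z/√N.

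Under Behavioral outcome measures the scheme is repeated for speech recognition, with the sentence "Additionally benefit scores will be determined by subtracting aided from aided scores". This is evidently a slip for aided from unaided.

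On when the baseline is taken, Section 4.2.1 says of QuickSIN: "SNR loss will be measured unaided at the initial assessment for all participants (prior to the random allocation process"). Section 4.2.2 extends this to DIN: "The DIN unaided and aided results will be measured following the same procedure as set for performing the QuickSIN". For APHAB, Section 4.1.1 says only "Participants will complete this questionnaire unaided at the end of the first visit".

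**The concern.** Two features of this plan weaken the non-inferiority comparison.

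1. **Use of baseline.** Subtraction fixes the baseline slope at 1, and comparing raw follow-up scores fixes it at 0. ANCOVA estimates the slope and in large samples is never less precise than either. With about 30 per arm, the width of the interval can decide whether its upper limit clears the margin.
2. **Data-driven choice of test.** The Shapiro-Wilk check has no stated level, and the plan does not say whether it is run on pooled data or by arm. Depending on the result, a visit is analysed on means or on ranks, so the two visits can end up on different quantities. The rank branch as planned (U, z and z/√N) gives nothing to set against 16.3 points or 1.8 dB. The t-test branch can give a difference in those units.

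IOI-HA is not affected: it has no baseline, and its test is fixed in advance.

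**Working it through.** **Inputs from the documents.** 60 participants, about 30 per arm (Section 3.3); two-sided 5% level (Section 5.1); margins of 16.3 points and 1.8 dB (Section 4.3). The documents give no SD, correlation or power, so there is no planned precision figure to reproduce.

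**Assumptions.** ρ is the correlation between unaided and aided scores, taken from 0.3 to 0.9. k is the aided SD divided by the unaided SD, taken from 0.7 to 1.43. Shapiro-Wilk is run at 5%.

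**Precision.** In units of the baseline variance:
- Var(benefit) ∝ 1 + k² − 2ρk
- Var(ANCOVA) ∝ k²(1 − ρ²)
- The difference is (1 − ρk)², which is never negative.

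At k = 1 the variance ratio is (1 + ρ)/2. With N = 60, estimating the slope multiplies it by (N − 3)/(N − 4) = 57/56 = 1.018.

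Worked case, APHAB with raw SD 20, ρ = 0.5, k = 1:
- Benefit: SD = 20√(2 × 0.5) = 20; SE = 20√(2/30) = 5.16; half-width = 2.002 × 5.16 = 10.3 points.
- ANCOVA: residual SD = 20√0.75 = 17.3; SE = 17.3 × √(2/30) × √1.018 = 4.51; half-width = 2.002 × 4.51 = 9.0 points.
- Width ratio: 9.03/10.34 = 0.87.

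Simulated width ratios to the benefit t-test (k = 1) and non-inferiority power per visit (true difference 0, upper 95% limit below the margin):

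| ρ | Width ratio, ordinary SE | Width ratio, HC3 | APHAB raw SD 20: t-test / HC3 ANCOVA | QuickSIN raw SD 3 dB: t-test / HC3 ANCOVA |
|---|---|---|---|---|
| 0.3 | 0.814 | 0.836 | 74% / 89% | 50% / 65% |
| 0.5 | 0.873 | 0.897 | 87% / 94% | 63% / 72% |
| 0.7 | 0.930 | 0.954 | 98% / 99% | 83% / 87% |
| 0.9 | 0.984 | 1.010 | 100% / 100% | 100% / 100% |

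Over the whole grid, the ANCOVA interval runs from 36% narrower (ρ 0.9, k 0.7) to 1% wider (ρ 0.8, k 1.25, where ρk = 1) with ordinary errors. With HC3 the range is about 34% narrower to 4% wider.

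Chance baseline imbalance is part of this same loss. The benefit estimate retains a fraction 1 − ρk of it: at k = 1, 70% at ρ 0.3 and 10% at ρ 0.9.

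**Standard errors.** The comparison covered 12 scenarios at ρ 0.5: splits of 30/30, 35/25 and 25/35, residual SD ratio between arms 1 or 1.5, and skewness 0 or 1. Coverage of the 95% ANCOVA interval was 94.9–96.0% with HC3 and 93.2–96.3% with ordinary errors. If the generator in Section 3.4 is simple 1:1 randomisation, a split of 35/25 or worse has probability 0.245.

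**The switch.** Suppose the data are normal and the two visits independent:
- Pooled check: P(exactly one visit rejected) = 2 × 0.05 × 0.95 = 0.095.
- Check by arm: P(a visit goes to ranks) = 1 − 0.95² = 0.0975, so P(exactly one) = 2 × 0.0975 × 0.9025 = 0.176.

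Simulation with correlated visits gives 0.097–0.099 (pooled) and 0.175–0.184 (by arm). Over three measures and two visits, if independent, at least one comparison goes to ranks with probability 1 − 0.95⁶ = 26% (pooled) or 1 − 0.9025⁶ = 46% (by arm).

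With skewness 0.5 in the raw scores, the two visits get different tests on benefit scores in 13–20% of trials (pooled) or 21–28% (by arm). At least one visit goes to Mann-Whitney in 14–22% or 23–32%. For raw aided scores, the visits differ in 30–38% or 33–40%.

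**APHAB timing.** Suppose SF participants rated their unaided difficulty 5 points worse because they already knew their arm (k = 1). The benefit comparison would then be biased by 5 points in favour of SF, and ANCOVA by 5ρ, i.e. 1.5 to 4.5 points. Timing therefore matters under either analysis.

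**The case against.** The strongest reply is that the covariate is an efficiency preference. The endpoint is defined as benefit, a t-test on benefit is unbiased, and every gain quoted rests on assumed values. On the primary endpoint the gain almost vanishes at ρ of 0.7 or more. All of this is true. It limits the claim to low or moderate ρ, which the documents neither support nor exclude.

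Other points that stand:
- A pre-specified interval on the mean benefit difference would also be in margin units. The absence of any planned interval is therefore a separate gap and is not an argument for ANCOVA.
- Ranks need not lack units: a Hodges-Lehmann shift with its interval is in points or dB. The plan does not include one, and adding it would still leave the visits on different quantities.
- The switch does not clearly inflate type I error for the null of no difference (simulated 0.048–0.059). Its harm is that the quantity estimated depends on the data.
- The largest switch figures concern raw scores, while the hypotheses concern benefit or improvement.
- HC3 is a choice that gives back part of the gain; ordinary errors performed acceptably.
- Table 1 places APHAB in the baseline column with QuickSIN, before the fitting visit. Only its order relative to allocation is left unstated.

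None of these is a reason to keep the switch or to leave a baseline already collected out of the model.

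**Conclusion.** The concern holds. It is a worthwhile and nearly free improvement, not a flaw that invalidates the trial. The planned comparison is unbiased but usually less precise than it could be, and its scale is left to a loosely specified normality test.

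At low to moderate ρ the loss can change the non-inferiority conclusion: power differs by about 15 percentage points at ρ 0.3 for both APHAB (raw SD 20) and QuickSIN (raw SD 3 dB). At ρ 0.9 it hardly matters. These sizes depend on assumed SDs, correlations and SD ratios. The objection to the switch does not depend on ρ being low, although its frequency rests on an assumed 5% Shapiro-Wilk level.

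**What to change.** - **Model.** At each visit, analyse the aided APHAB, QuickSIN and DIN scores by ANCOVA. Include arm, and as the only covariate the unaided baseline of the same measure, fixed in advance.
- **Estimate and sign.** Report SF minus AF in aided score. Because benefit is unaided minus aided, this equals AF minus SF in benefit, which is p0 − p1 in the alternative hypotheses of Section 4.3. (The primary null there swaps the two labels and should be aligned.) For QuickSIN the direction is stated: "higher SNR loss indicates a poorer outcome". For DIN, state that lower is better, which is assumed here.
- **Interval.** Use a two-sided 95% confidence interval on residual degrees of freedom, and compare its upper limit with 16.3 points or 1.8 dB. HC3 standard errors are suggested as protection against unequal arms and variances. Ordinary errors are acceptable if named in advance. Keep the chosen method whatever the residuals look like.
- **Switch.** Delete it. Keep Mann-Whitney on benefit scores as a sensitivity analysis, with a Hodges-Lehmann shift and interval so that it can be read against the margin.
- **Text.** State that the unaided APHAB is completed before allocation, and correct the subtraction sentence under Behavioral outcome measures. IOI-HA stays as planned.

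Which visit and which APHAB score are primary is a separate matter.

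**Cost.** SAP wording, one sentence on APHAB timing, and one degree of freedom (57 instead of 58). In unfavourable cases the interval is about 1% wider with ordinary errors or 4% wider with HC3. No new data are needed.

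### A Shapiro-Wilk test chooses t-test or Mann-Whitney variable by variable, so the 2- and 6-week results may rest on different quantities, and neither branch specifies a comparison with the margin

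*Combined protocol and SAP*

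**What the plan says.** Section 4.3 sets the primary hypothesis on APHAB benefit at both 2 and 6 weeks: self-fit is to be non-inferior to audiologist-fit within 16.3 points. The speech-in-noise hypothesis uses 1.8 dB for QuickSIN and DIN. Section 5.1 sets a two-sided 5% level.

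Section 5.3, Self-reported hearing aid difficulties, covers the APHAB. It takes raw scores at every time point, "along with the calculated benefit scores (unaided-aided) will be continuous variables". It then says "Data will be assessed for normality using the Shapiro" Wilk test. The two branches follow: "For non-normally distributed variables, non-parametric comparisons between groups will be completed using the Mann Whitney" *U* test, and "For normally distributed variables, comparisons will be done using the independent samples" *t*-test. For the t-test branch the effect size is Cohen's d, calculated only where the difference is significant. For the other branch, "Effect sizes for non-normally distributed variables will be calculated using effect size" r, defined as z/√N.

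Section 5.3, Behavioral outcome measures, repeats the rule for the speech tests: "All variables are continuous and will be assessed for normality".

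The Shapiro-Wilk threshold is not given. Nor does the plan say whether the test is run in each arm, on the pooled data or on residuals. Means, SDs, medians and quartiles are promised only for baseline characteristics.

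**The concern.** A non-inferiority claim with a numerical margin needs an estimate on the margin's scale, with a confidence limit, obtained by a method fixed before the data are seen. Here the method is an outcome of the data. APHAB benefit at 2 weeks and at 6 weeks are separate variables, so each goes through its own normality test and each can take a different branch.

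The t-test concerns a difference in means. Mann-Whitney concerns the relative ordering of the two groups. If the visits split, one hypothesis is answered by two different quantities. Wherever the Mann-Whitney branch is taken, the specified outputs (a p-value and a unit-free r) cannot be set against 16.3 points or 1.8 dB. Because the threshold and level of the pre-test are open, the selection rule itself could still be settled after unblinded data are available.

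**Working it through.** **1. What each branch delivers, set against section 4.3**

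| | t-test branch | Mann-Whitney branch |
|---|---|---|
| Test | Independent samples t | Mann-Whitney U |
| Effect size | Cohen's d, only if significant | r = z/√N |
| Estimate in points or dB with CI | Not specified | Not specified (no Hodges-Lehmann shift) |
| Comparison with 16.3 or 1.8 | Not specified | Not specified |

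The last two rows are the same on both branches. What belongs to the pre-test alone is that the method depends on the data and can differ between visits.

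**2. How often the visits would split**

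From the plan: about 30 per arm (section 3.3) and two visits (section 4.3). Assumed, because the documents are silent: a 5% Shapiro-Wilk threshold, testing per arm (switch if either arm rejects) or pooled, correlation 0.6 between visits, the same distribution shape in both arms, and no true group difference.

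A hand check for exactly normal data, treating visits as independent:
- Per arm: switch probability at one visit = 1 − 0.95² = 0.0975. Different tests at the two visits = 2 × 0.0975 × 0.9025 = 0.176.
- Pooled: 2 × 0.05 × 0.95 = 0.095.

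Simulation at correlation 0.6 gives the following. Skewed data are gamma with shape 8 (skewness 2/√8 = 0.71) and shape 4 (skewness 2/√4 = 1.0). Ranges cover repeated runs.

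| Shape of benefit | Different tests, per arm | Different tests, pooled |
|---|---|---|
| Normal | 18–19% | 9–11% |
| Skewness 0.7 | 42–44% | 44–45% |
| Skewness 1.0 | 38–39% | 30–32% |

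The normal row agrees with the hand check. In the largest run (4,000 trials per shape, per arm), Mann-Whitney was used at one visit or more in 19%, 66% and 89% of trials. The Monte Carlo standard error for a rate of 0.181 is √(0.181 × 0.819/4000) = 0.006.

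Sensitivity to the assumptions:
- Correlation 0.5 or 0.7, per arm or pooled: about 9–19%, 41–47% and 28–41%.
- Threshold 1%, per arm, correlation 0.6: about 4%, 31% and 45%.

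**3. Whether the t-test branch settles non-inferiority**

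Simulated with 30 per arm, normal data and a true self-fit deficit of 10 points. A trial is counted if the t-test is non-significant at 5% and the upper 95% limit of audiologist-fit minus self-fit is not below 16.3.
- SD 20 (assumed): 29.7% of trials.
- SD 25 (assumed): 51.3% of trials.

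A non-significant t-test therefore does not stand in for the comparison with the margin. Always landing on the t-test branch would not repair the plan.

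**The case against.** A reader might infer that the switch to Mann-Whitney is what removes the needed estimate, and that the margin would be usable if normality were never rejected. The documents do not support this: section 5.3 promises no mean difference with an interval on the t-test branch either, and Cohen's d only after a significant result. The absent non-inferiority comparison is a wider gap that the pre-test did not create.

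A reader might also infer that the margin cannot be applied once Mann-Whitney is used. That is too strong. A rank analysis can carry a Hodges-Lehmann shift with a confidence interval in APHAB points. The plan does not specify one, and if it did, the estimate would be a location shift and not the mean difference used at the other visit.

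Nor does section 4.3 state that the margins are differences in means. It writes p0 and p1 without defining them, and ties the margins to the smallest observable change and to a critical difference score. A mean difference is the natural reading, but it is an inference.

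Finally, the rule is written in advance, is a common convention, and inflates type I error only slightly. All of that stands. The switching rates also rest on assumptions that the documents neither give nor contradict; in particular, nothing in them supports a skewness of 0.7 or 1.0 for a difference score. What survives these objections is that the method can differ by visit within one hypothesis, and that the rank branch as written yields nothing in scale units.

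**Conclusion.** The concern holds in a limited form. For APHAB, QuickSIN and DIN the method is chosen variable by variable by an under-specified normality test, so the analysed quantity is not fixed in advance. Under the 5% threshold and correlation 0.6, the chance that the two visits use different tests is about 9–19% for exactly normal benefit, 42–45% at skewness 0.7 and 30–39% at skewness 1.0. These figures show that a split is plausible; they do not forecast this trial. The textual reading is secure, and the rates are illustrative only.

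The harm is an unstable target for a margin-based claim, not a material rise in false positives. It is secondary to the missing comparison with the margin, and both should be repaired together. The change is advisable: it bears on the primary endpoint and on both speech-in-noise outcomes.

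**What to change.** In section 5.3, remove the Shapiro-Wilk test as a selector and name one analysis for APHAB, QuickSIN and DIN benefit at both visits:
- **Model:** a linear model of benefit on group, adjusted for the baseline (unaided) score, which is already collected.
- **Estimate:** the between-group difference in mean benefit, audiologist-fit minus self-fit, with a two-sided 95% CI at each visit.
- **Decision:** non-inferiority if the upper limit is no greater than the stated margin (16.3 points for APHAB, 1.8 dB for QuickSIN and DIN).
- **Sensitivity:** Mann-Whitney with a Hodges-Lehmann CI, or a bootstrap CI for the mean difference, reported whatever the distribution looks like.
- **Diagnostics:** normality plots, with no effect on the choice of method.

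Section 4.3 should state that p0 and p1 are mean benefits, with the same labels throughout. Deleting the pre-test without adding the estimate and decision lines would not be enough.

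The cost is SAP wording and slightly more analysis; the linear model runs in the stated software. The change does not in itself require a different sample size. For an unadjusted comparison with a true difference of 0, 30 per arm gives 80% power against 16.3 up to an SD of 16.3/((1.960 + 0.842) × √(2/30)) ≈ 22.5 points. The documents give no SD against which to judge that.
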